3.9.3 Randomization (Visit 3; Day 0)

Randomization visit procedures will aim at collecting data that will be utilized as baseline measures for the statistical analysis for primary and secondary outcomes, and exploratory analyses.

- Concomitant medications
- Adverse events
- Study drug compliance
- Vital signs, weight, height, and orthostatics
- OABO
- 3-day VD assessment
- PPBC
- CQ
- UPDRS-6
- MoCA
- Map Search
- Hopkins Verbal Learning Test (HVLT)
- Trail Making Test (TMT) parts A and B
- Beck Anxiety Inventory (BAI)
- Beck Depression Inventory version II (BDI-II)
- Epworth Sleepiness Scale (ESS)
- Parkinson Fatigue Scale (PFS)
- Parkinson's Impact Scale (PIMS)
- Study drug dispense

At the conclusion of the randomization visit, subjects will be randomized in a double-blind fashion in a ratio of 2:1 to mirabegron 25 mg daily vs. placebo. Study drug will be administered in the form of 1 mirabegron 25 mg extended release matching placebo tablet daily (placebo arm) or 1 mirabegron 25 mg extended release tablet daily (active treatment arm). Thus all subjects will continue to receive 1 tablet daily. Sufficient study drug will be dispensed to last until Visit 6.

3.9.4 Low-dose phase maintenance visit (Visit 4 - telephone call; Day 7)

The purpose of this telephone call is to assess adverse events and medication compliance. It can be conducted via telephone interview.

- Concomitant medications
- Adverse events
- Study drug compliance

3.9.5 Dose escalation visit (Visit 5; Day 14)

The purpose of this visit is to assess adverse events, medication compliance, and obtain interim measures for analyses.

- Concomitant medications
- Adverse events
- Study drug compliance
- Vital signs, weight, height, and orthostatics
- Physical Examination
- Neurological Examination
- ECG
- UPDRS
- Urologic examination
- PVR
- Urinalysis
- OABQ
- 3-day VD assessment
- PPBC
- Study drug dose escalation instructions

The urologic examination, PVR, and urinalysis may be obtained at a separate visit, within the 3 days preceding scheduled Visit 5. At the conclusion of Visit 5, subjects will be instructed to increase the dose to ge2 mirabegron 25 mg extended release - matching placebo tablets daily (placebo arm) or 2 mirabegron 25 mg extended release tablets daily (active treatment arm). Thus all subjects will begin receiving 2 identical looking tablets daily.

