3.9.6 High-dose phase maintenance visit (Visit 6; Day 42)

The purpose of this visit is to establish interim overall tolerability of the medication, medication compliance, and obtain interim measures for analysis.

- Concomitant medications
- Adverse events
- Study drug compliance
- OABQ
- 3-day VD assessment
- PPBC
- Study drug dispense

At the conclusion of Visit 6, subjects will be dispensed mirabegron 25 mg tablets or matching placebo. Study drug will be administered in the form of 2 mirabegron 25 mg, matching placebo tablets daily (placebo arm) or 2 mirabegron 25 mg tablets daily (active treatment arm). Thus all subjects will continue to receive 2 identical looking tablets daily. Sufficient study drug will be dispensed to last until the end of treatment visit (Visit 7).

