3.9.9 Unscheduled visit

Unscheduled visits can be conducted at the Investigator's discretion. Procedures during these visits will be focused to the problem that precipitated the visit. If a subject develops intolerable side effects during the treatment period, but wishes to continue in the study, he/she may come in for an unscheduled visit. A dose reduction is permitted only once during treatment and only after the dose escalation to mirabegron daily dose of 50 mg vs. placebo. The dose can be decreased at that time to 25 mg of mirabegron vs. placebo. Subjects that require such dose reduction will be receiving one tablet daily. Further dose reductions will not be permitted, and, if deemed necessary, subjects will be brought in for early termination.

Changes in the antiparkinsonian agents or cognitive enhancers will only be permitted to a limited degree, and only if, in the opinion of the investigator, are not likely to alter the outcome measures of the study. Naturally, if these medication changes are triggered by worsening of the PD or cognitive symptoms, such worsening will have to be logged as an adverse event or serious adverse event as appropriate.

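### After the step-up to two tablets at Day 14, made by instruction only, the first scheduled adverse-event and compliance check is at Day 42, 40% of the way through the high-dose phase

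*Combined protocol and SAP*

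**What the plan says.** Section 3.9.5 makes the dose change at the end of the Day 14 visit: "At the conclusion of Visit 5, subjects will be instructed to increase the dose". The only drug item in that visit's procedure list is "Study drug dose escalation instructions"; dispensing is not listed. The tablets come from the randomization visit, where section 3.9.3 states "Sufficient study drug will be dispensed to last until Visit 6". Table 1, read with the section 3.9 lists, places dispensing at Visits 2, 3 and 6 only.

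The one-tablet start is followed by a Day 7 call. Section 3.9.4 explains: "The purpose of this telephone call is to assess adverse events and medication compliance". Visit 5 repeats those checks on Day 14, before the tablets are doubled. The first scheduled check on two tablets is Visit 6 (section 3.9.6, Day 42): "The purpose of this visit is to establish interim overall tolerability of the medication, medication compliance". The next is Visit 7 (section 3.9.7, Day 84).

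Between visits, section 3.9.9 allows unscheduled visits at the Investigator's discretion. It adds that a subject with intolerable side effects who wants to stay in the study can ask to be seen: "he/she may come in for an unscheduled visit". Section 3.6 has the need for a caregiver assessed at screening and that person's commitment secured. Section 3.3 item 8 accepts a care partner as an alternative to completing the assessments unaided.

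**The concern.** The primary objective is tolerability, and the move from one to two tablets is the only planned dose change. The plan schedules a call a week after the first double-blind tablet, yet nothing comparable after the doubling, and gives no reason for the difference.

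Two things are at stake. First, adverse events are summarized by group (section 7.4.4). Events between Day 14 and Day 42 that the subject did not think worth a visit would be reported from memory over up to four weeks, in a population selected for a screening MoCA of 19 to 28, or up to 29 on cognitive enhancers. Second, the step-up depends on the subject changing the number of tablets taken from a supply already at home. Section 6.1.6 itself anticipates confusion, because the package insert says one tablet a day. A subject who did not make the change would not be found by any scheduled procedure until Day 42.

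**Working it through.** The documents print visit days but not the intervals, so there is no stated figure to reproduce. No visit windows are given, and nominal days are used throughout.

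**Inputs.** Visit 3 = Day 0, Visit 4 = Day 7, Visit 5 = Day 14, Visit 6 = Day 42, Visit 7 = Day 84 (Table 1 and section 3.9). One tablet daily from Visit 3 to Visit 5 and two from Visit 5 to Visit 7 (Table 4). Each active tablet is 25 mg.

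**Intervals between scheduled contacts**

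| Interval | Tablets daily | Days |
|---|---|---|
| Visit 3 to 4 | 1 | 7 - 0 = 7 |
| Visit 4 to 5 | 1 | 14 - 7 = 7 |
| Visit 5 to 6 | 2 | 42 - 14 = 28 |
| Visit 6 to 7 | 2 | 84 - 42 = 42 |

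**Share of the high-dose phase before the first check.** The phase lasts 84 - 14 = 70 days, and 28 / 70 = 40%.

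**Exposure of an active subject who stays on one tablet until Day 42.** Assigned for the whole phase: 70 × 50 mg = 3500 mg. Shortfall by Day 42: 28 × 25 mg = 700 mg, and 700 / 3500 = 20%. Within the 28 days, the subject takes 28 of the 56 tablets due (50%).

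**What the tablet count would show.** From Visit 3 to Visit 6 the schedule uses 14 × 1 + 28 × 2 = 70 tablets; a subject who never stepped up would have used 42. The 28 extra returned tablets are visible under section 6.1.10, but the first scheduled count after the step-up is on Day 42.

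**With a contact on Day 21.** The first check falls at 7 / 70 = 10% of the phase. The shortfall by then is 7 × 25 mg = 175 mg, or 175 / 3500 = 5%. That is the best case: it assumes the subject reports the tablet number correctly and the change is made that day.

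**A gap in the compliance definition.** Section 6.1.10 counts missed doses (more than 4 in 28 days), while section 6.1.6 has both tablets taken together as a single dose. Whether one tablet out of two counts as a missed dose is not stated, so a direct question about tablets per day adds information that the definition does not clearly capture.

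**The case against.** The case against is that the plan has safeguards and that the consequences are easily overstated.

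- **Safeguards exist.** Unscheduled visits may be called by the Investigator, not only requested by the subject. The need for a caregiver is assessed at screening, and section 3.4 item 16 excludes anyone judged unable to follow the procedures. This stands: it would be wrong to infer that subjects go unchecked for 28 days. What is absent is a scheduled check. A caregiver is not required for everyone, and an unscheduled visit needs someone to notice a problem first.
- **The primary result.** A reader might infer that under-exposure pulls the MoCA comparison toward equivalence and so favors the hypothesis. The documents do not support this. MoCA is analyzed as change from Visit 3 to Visit 7. The Day 42 count can expose a missed step-up with 42 of the 70 high-dose days (60%) remaining, and the prescribing information puts steady state within 7 days of daily dosing. No link from a 20% cumulative shortfall to a Day 84 score is available. One-tablet exposure at Day 84 is also already possible under the dose reduction in section 6.1.8.
- **Where contact is sparsest.** A reader might infer that contact is thinnest immediately after the step-up. It is not: the longest on-treatment gap is the 42 days from Visit 6 to Visit 7. Contact is thinner after the step-up than before it, and no more than that.
- **Population and recall.** Section 3.10.1.1 treats a MoCA of 26 or above as normal, so some eligible subjects are not impaired by that cutoff. No recall-failure rate is given, and both arms follow the same schedule. The under-counting of milder events is therefore a plausible risk, not a measured one.
- **Form of the instructions.** Section 3.9.5 does not say whether they are oral or written. Written instructions would lessen the reliance on memory.

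The visit dates, the absence of dispensing at Visit 5 and the 28-day interval are not in dispute.

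**Conclusion.** The point holds as a weakness in safety data capture and exposure verification. The plan schedules its first adverse-event and compliance check on two tablets after 28 of 70 high-dose days (40%), against 7 days after the one-tablet start. The existing provisions do not guarantee that milder events or a missed step-up are found sooner. The exposure at risk is up to 700 mg of 3500 mg (20%) per affected active subject by Day 42. This assumes nominal visit days and a subject who was meant to move to two tablets and took one throughout.

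The number of subjects affected cannot be determined from the documents, and neither can any effect on the Day 84 MoCA. No sample size, alpha or power figure changes. This is an inexpensive improvement worth making, not a defect that invalidates the analysis.

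A related inconsistency affects who counts as having missed the step-up. The Synopsis (Dosage and Administration) keeps subjects with side effects that still allow continuation on one tablet, whereas sections 3.9.5 and 6.1.6 move all subjects to two. These passages must be reconciled.

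**What to change.** Add one telephone data-collection contact about a week after Visit 5 (Day 21). Repeat the three Visit 4 items: concomitant medications, adverse events and study drug compliance. Ask explicitly how many tablets are being taken each day, and include the care partner where there is one. No dose rule changes.

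Cost: about 30 short coordinator calls, one CRF page and one column in Table 1, with a little extra staff time and subject burden. The call relies on self-report without a tablet count, so it reduces undetected under-exposure but does not remove it. It leaves the 42-day gap from Visit 6 to Visit 7 as it is.

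In the same amendment, reconcile the Synopsis with sections 3.9.5 and 6.1.6 on who goes to two tablets, so that the tablet number reported on Day 21 can be compared with an unambiguous assigned number.

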3.9.6 High-dose phase maintenance visit (Visit 6; Day 42)

The purpose of this visit is to establish interim overall tolerability of the medication, medication compliance, and obtain interim measures for analysis.

- Concomitant medications
- Adverse events
- Study drug compliance
- OABQ
- 3-day VD assessment
- PPBC
- Study drug dispense

At the conclusion of Visit 6, subjects will be dispensed mirabegron 25 mg tablets or matching placebo. Study drug will be administered in the form of 2 mirabegron 25 mg, matching placebo tablets daily (placebo arm) or 2 mirabegron 25 mg tablets daily (active treatment arm). Thus all subjects will continue to receive 2 identical looking tablets daily. Sufficient study drug will be dispensed to last until the end of treatment visit (Visit 7).

3.9.7 End of treatment / Early termination visit (Visit 7; Day 84)

During Visit 7, screening and baseline safety and tolerability as well as efficacy and outcome measures will be repeated.

- Concomitant medications
- Adverse events
- Study drug compliance
- Vital signs, weight, height, and orthostatics
- Physical Examination
- Neurological Examination
- ECG
- UPDRS
- Blood samples for chemistry and hematology (Na, K, Cl, HCO₃, blood glucose, BUN, creatinine, GFR, AST, ALT, total bilirubin, Alkaline phosphatase, GGT, CBC with differential and platelets)
- Urinalysis
- OABO
- 3-day VD assessment
- PPBC
- CQ

- UPDRS-6
- MoCA
- Map Search
- Hopkins Verbal Learning Test (HVLT)
- Trail Making Test (TMT) parts A and B
- Beck Anxiety Inventory (BAI)
- Beck Depression Inventory version II (BDI-II)
- Epworth Sleepiness Scale (ESS)
- Parkinson Fatigue Scale (PFS)
- Parkinson's Impact Scale (PIMS)

If a subject at any point during the study requests to withdraw from treatment, they should return for an early termination visit. The procedures of visit 7 and visit 8 can be combined in a single visit for early termination subjects. It would be desirable that subjects continue to receive study drug until early termination procedures can be completed.

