Rationale: There is a high prevalence of OAB symptoms among patients with Parkinson's disease and a lack of pharmacotherapies with an acceptable side effect profile. Specifically, available anticholinergic medications have a high risk of cognitive side-effects, which preclude their use in PD patients with CI. PD can also cause a number of non-motor symptoms that are likely to be adversely affected by the currently available anticholinergic agents. Mirabegron is the first pharmacologic treatment which may not exacerbate CI, constipation, orthostatic hypotension (OH), somnolence, and dry mouth in PD.

Objectives:

Primary Objective:

• To assess cognitive tolerability of mirabegron while treating OAB in PD patients with CI.

Secondary Objectives:

- To assess the efficacy of mirabegron for treating OAB symptoms in PD with CI.
- To assess the effect of mirabegron on health related quality of life in PD patients with OAB symptoms and CI.
- To assess the effect of mirabegron on excessive daytime sleepiness in PD patients with OAB symptoms and CI.

Exploratory analyses:

- To assess the effects of mirabegron on orthostatic changes in blood pressure in PD patients with OAB symptoms and CI.
- To assess the effect of mirabegron on depressive and anxiety symptomatology, excessive salivation, and constipation in PD patients with OAB symptoms and CI.
- To assess effects of mirabegron on PD motor symptom severity in PD patients with OAB symptoms and CI.

Study Design:

This is a pilot study conducted in one study center. Study design will be a randomized, double-blind, placebo-control study. Subjects will receive a two-week, single-blind placebo run-in followed by 2 weeks of a 1:2 randomized double-blind phase (placebo:25 mg mirabegron), followed by 10 weeks dose escalation (placebo:50 mg mirabegron), followed by a two-week washout period.

Study Duration:

Maximum participation will be 20 weeks, consisting of 2-4 weeks screening period, 2 weeks of placebo run-in, 12 weeks of double-blind placebo-controlled treatment, and 2 weeks of safety follow up.

Study Population:

Adult ambulatory outpatients with PD, CI, and OAB symptoms.

Statistical Analysis:

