Descriptive statistics will be performed. The primary group for analysis will consist of all subjects who received at least one dose during the double-blind placebo-controlled phase. Analyses will compare change from randomization (visit 3) to end of treatment (visit 7). Tests of equivalence will be performed on primary, secondary and exploratory outcomes, with significance level of p<.05.

Study Procedures:

Refer to the Study Schedule/Flowchart, below.

Number of Subjects: 30 (20 active treatment, 10 placebo group).

Eligibility criteria:

INCLUSION CRITERIA:

- 1. Aged 25-80 at screening. Subjects older than 80 will be allowed at the discretion of the PI.
- 2. Ambulatory (defined as able to ambulate at least 10 meters, with or without assistance).
- 3. Clinical Diagnosis of PD based on the United Kingdom Brain Bank diagnostic criteria for PD.
- 4. At baseline visit (Visit 2) patients must have:
 - a. At least 8 micturitions per 24 hours and

- b. At least 3 urgency episodes per 3-day diary.
- 5. A MoCA score between 19 and 28 (inclusive) at screening. For those on cognitive enhancers (donepezil, rivastigmine, memantine, galantamine) a MoCA score between 19 and 29 (inclusive) at screening.
- 6. Provide informed consent to participate in the study and understand that they may withdraw their consent at any time without prejudice to their future medical care.
- 7. Be cognitively capable, in the opinion of investigator, to understand and provide such informed consent.
- 8. Be cognitively capable to complete the required questionnaires and assessments, OR have a care partner who is willing and capable to assist them in the completion of these tasks.
- 9. Be on a stable regimen of antiparkinson's medications at least 30 days prior to screening, and be expected to remain on a stable dose for the duration of the study.
- 10. If taking cognitive enhancers (donepezil, rivastigmine, memantine, galantamine), must be on stable dose at least 30 days prior to screening, and be expected to remain on a stable dose for the duration of the study.

EXCLUSION CRITERIA:

- 1. Known or suspected alcohol or substance abuse in the preceding 12 months.
- 2. Women who are pregnant or breastfeeding.
- 3. Women of childbearing potential (WOCP) who are not using at least one method of contraception.
- 4. Patients with severe renal impairment ($CL_{cr} \le 29 \text{ mL/min}$, or eGFR ≤ 29 mL/min/1.73 m²), or moderate or severe hepatic impairment (Child-Pugh classes B or C).

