3.9.8 Safety follow up visit (Visit 8; Day 84+14)

The purpose of this visit will be to ensure lack of any delayed adverse events. These procedures can be combined with visit 7 for early termination subjects who request withdrawal from treatment.

- Concomitant medications
- Adverse events
- Vital signs, weight, height, and orthostatics
- Physical Examination
- Neurological Examination
- Urological Examination
- Urinalysis
- UPDRS
- PVR
- PPBC
- Serum pregnancy test (SPT) for WOCP

The urologic examination, PVR, and urinalysis may be obtained at a separate visit, within the 3 days preceding scheduled Visit 8.

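### An early terminator's Visits 7 and 8 may be merged while the subject is still dosing, leaving 0 scheduled off-drug days of safety follow-up against 14 for a completer

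*Combined protocol and SAP*

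**What the plan says.** Section 3.9.8 places Visit 8 at Day 84+14 and gives its aim: "The purpose of this visit will be to ensure lack of any delayed adverse events". Table 4 in section 6.1.7 shows no study drug between Visits 7 and 8, and the synopsis describes this interval as a two-week washout.

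For subjects who stop early, section 3.9.7 has three sentences in a row. The first asks anyone who wants to stop treatment to come back for an early termination visit. The second gives the permission to merge: "The procedures of visit 7 and visit 8 can be combined in a single visit for early termination subjects". The third, on dosing in the meantime, is a preference and not a requirement: "It would be desirable that subjects continue to receive study drug until early termination procedures can be completed".

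Section 3.9.8 repeats the permission in narrower words: "These procedures can be combined with visit 7 for early termination subjects who request withdrawal from treatment".

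Section 3.9.9 brings in for early termination those subjects who would need a second dose reduction. It does not say whether their visits may be merged.

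**The concern.** The three sentences of section 3.9.7, followed together, put the check for delayed events on about the last day of dosing. An event that appears after the drug is stopped cannot be seen at such a visit, nor can the resolution of an event off drug. From then on, either is recorded only if the subject reports it or the investigator calls the subject back.

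This matters because subjects who ask to stop can include those stopping for side effects, and whether an event clears off drug helps the attribution that section 4.0 requires. Reliance on self-report is also less comfortable here than in most trials. Subjects are selected for impaired cognition, and inclusion criterion 8 foresees that some will need a care partner to complete assessments. What is at stake is the safety follow-up of individual subjects.

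**Working it through.** **Scheduled off-drug time.** Table 1 puts Visit 7 at day 84 and Visit 8 at day 98.

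- Completer: 98 - 84 = 14 days. This reproduces the Day 84+14 of section 3.9.8 and the two-week washout of the synopsis.
- Early terminator, visits merged, dosing continued to the visit: the last dose falls on or about the visit day, so 0 days.
- Early terminator, visits merged, drug stopped before the visit: some off-drug days, but by circumstance and not by schedule.

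Scheduled contacts after the last dose: 1 for a completer (Visit 8), 0 for a subject merged while dosing, and 1 for that subject under the fix below.

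**Pharmacokinetic context only.** Appendix I, section 12.3, gives a terminal half-life of about 50 hours. Fourteen days is 14 x 24 = 336 hours, and 336 / 50 = 6.72 half-lives. The fraction of drug left is 0.5^6.72 = 0.0095, or about 1%. A subject who has taken mirabegron daily for at least 7 days and is still dosing is at steady state by the same section. These figures show how different the two visits are. They do not measure adverse-event risk, and the gap does not depend on them.

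**Other provisions that might fill the gap.**

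- Section 3.5: best efforts for an early termination visit and safety follow-up, but only after withdrawal of consent, with no interval, and without removing the permission to merge.
- Section 3.9.9: unscheduled visits, at the investigator's discretion.
- Section 3.11.6: repeat of clinically important abnormal laboratory results. This is mandatory, but it applies only to abnormal results and has no fixed date.
- Section 5.0: post-study adverse events go to the monitoring committee, but no contact is set up to find them.
- Section 6.1.10: a dose held for an adverse event is an acceptable miss. This bears on dosing and adds no contact.

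Each is discretionary, conditional or undated, or adds no contact. None schedules one after the last dose.

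**Who is covered.** Subjects who request withdrawal from treatment are covered by both sections. For those brought in under section 3.9.9 the text is ambiguous: the merge sentence in 3.9.7 refers to early termination subjects without qualification, while 3.9.8 restricts it to those who request withdrawal.

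**Endpoints.** The synopsis says "Analyses will compare change from randomization (visit 3) to end of treatment (visit 7"), so nothing measured at Visit 8 enters the change scores. Section 7.3 excludes withdrawn participants from analyses.

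**The case against.** The strongest reply is that this is a deliberate and optional accommodation. Zero days arises only if three things coincide: the subject stops early, the site chooses to merge, and the subject keeps dosing until the visit. Subjects may leave at any time, so a second contact cannot be compelled. Merging also has a benefit: post-void residual is scheduled only at Visits 1, 5 and 8, so a merged visit secures a measurement that a leaving subject might otherwise miss. The drug is approved and given at labelled doses, and its label reports that blood pressure increases reversed after stopping. No delayed or withdrawal reaction from the label is at issue here. All of this stands. It argues for keeping the merge option and for modest weight, but it does not supply the missing contact.

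Two stronger readings are tempting and should be resisted.

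- A reader might infer that merging breaks a promise in the synopsis, which lists "and 2 weeks of safety follow up". That phrase is part of a sentence on maximum participation. It does not set a minimum owed to every subject who leaves.
- A reader might infer biased results. The merge permission is the same in both arms of a blinded trial, and the documents give no dropout or merging rate by arm. No bias in the between-arm comparison is shown.

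**Conclusion.** The gap is real and narrow. The plan permits a subject merged while dosing to have 0 scheduled off-drug days, against 14 for a completer, and such a visit cannot meet Visit 8's stated aim. The conclusion rests on the wording of sections 3.9.7 and 3.9.8 and on finding no scheduled contact after the last dose elsewhere in the plan. It assumes that the site uses the permission and that the subject follows the dosing preference. It does not say that early terminators as a rule lose their follow-up.

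The number of subjects affected cannot be estimated, because no dropout rate is given. Missed events cannot be estimated either, because no delayed-event rate is given. This is a cheap improvement to individual safety follow-up and leaves the statistical conclusions where they are.

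**What to change.** Keep the merge option and add two sentences to sections 3.9.7 and 3.9.8.

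1. Any early terminated subject who took double-blind drug and has no separate Visit 8 about 14 days after the last dose receives a telephone contact at that time, covering adverse events and concomitant medications. The interval runs from the last dose taken, not from Day 84. The Visit 4 call in section 3.9.4 can be reused: "The purpose of this telephone call is to assess adverse events and medication compliance", and its checklist already includes concomitant medications.
2. The preference for continued dosing does not apply when the subject stops for an adverse event or intolerance. This makes explicit what section 6.1.10 implies by accepting held doses.

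The first sentence also settles the ambiguity over section 3.9.9, because it applies whatever the route to early termination.

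The cost is the wording plus one call for each early terminated subject without an off-drug Visit 8, which is a wider group than merged subjects alone. As an illustration only, if 10 to 30% of the 30 subjects left early (an assumed range), that is 0.10 x 30 = 3 to 0.30 x 30 = 9 calls at most. No procedure is lost. Some subjects will decline the call, and the attempt should then be recorded.
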